Within each study cohort (ie, infants aged 1 month to <1 year and in patients aged 1 to <2 years), the primary study objective is:

Version 2.0, 10 February 2022

(1) to estimate the incidence of prespecified outcomes of interest as described below under variables in patients with a diagnosis of GERD with or without EE and treated with IV pantoprazole.

The two secondary objectives are as follows: (1) to estimate the incidence of prespecified outcomes of interest in patients treated with IV pantoprazole without a diagnosis of GERD or EE, and (2) to provide the frequency of the 25 most common diagnostic codes occurring within 30 days prior to or on the date of initiation of IV pantoprazole through 90 days of the last treatment with IV pantoprazole in patients with a diagnosis of GERD (regardless of EE diagnosis).

Study design

Retrospective cohort study using Optum's longitudinal electronic health records (EHR) repository from the United States (US).

Study population

Two separate cohorts, ie, infants aged 1 month to <1 year and patients aged 1 to <2 years who received at least one administration of IV pantoprazole during a study period of 01 January 2007 to 31 December 2020 and those enrolled in the database for at least 30 days prior to the date of first administration of IV pantoprazole will be identified from the Optum's longitudinal EHR repository. In both cohorts, patients with International Classification of Diseases, Ninth Revision, Clinical Modification (ICD-9-CM) or International Classification of Diseases Tenth Revision, Clinical Modification (ICD-10-CM) codes indicating a preterm birth will be excluded. Within each cohort, 3 subgroups will be identified: (1) patients with ICD-9-CM or ICD-10-CM codes for GERD with EE, (2) patients with ICD-9-CM or ICD-10-CM codes for GERD but without EE, and (3) patients without diagnosis codes for GERD or EE.

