9. RESEARCH METHODS

9.1. Study design

This will be a retrospective cohort study with no comparator group. No a priori hypotheses are specified. Descriptive analyses including an estimation of incidence rates will be performed.

9.2. **Setting**

The study will be conducted using Optum's longitudinal integrated EHR from the US¹, which is described in Section 9.5 This data source includes data from adjudicated administrative insurance claims, inpatient electronic health records, as well as outpatient EHR enabling capture of exposure to IV pantoprazole in the study population of interest. The study period will be defined from 01 January 2007 to 31 December 2020.

9.3. **Study population**

Two separate cohorts, ie, infants aged 1 month to <1 year and patients aged 1 to <2 years will be identified during the study period using the following inclusion and exclusion criteria.

9.3.1. **Inclusion criteria**

Patients must meet all of the following inclusion criteria to be eligible for inclusion in the study:

- 1. At least one administration of IV pantoprazole during the study period from January 1, 2007 to December 31, 2020, and
- 2. For the cohort of infants aged 1 month to <1 year (Cohort 1): Age 1 month to <1 year on the index date (ie, the date of first administration of IV pantoprazole); For the cohort of patients aged 1 to <2 years (Cohort 2): Age 1 to <2 years on the index date.
- 3. Patients must be enrolled in the database for at least 30 days prior to the index date

In addition to this 30-day lookback window, patients will be further excluded based on the occurrence of a history of outcomes of interest identified in Table 3 occurring prior to the index date.

9.3.2. **Exclusion criteria**

Patients meeting any of the following criteria will not be included in the study:

1. Patients with any of the following ICD-9-CM or ICD-10-CM codes occurring prior to or on the index date indicating a preterm birth or birth weight less than 2.36 kilograms will be excluded:

ICD-9-CM codes: 765.01-765.08; 765.10-765.19; 765.21-765.28

ICD-10-CM codes: P07.21-P07.26; P030-P039; P07.01-P07.03; P07.14-P07.18

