The cut-off of birth weight less than 2.36 kilograms is defined based on a birth weight that is less than third percentile weight for males at birth obtained from Centers for Disease Control and Prevention (CDC) infant weight-for-age charts (available at URL: https://www.cdc.gov/growthcharts/html charts/wtageinf.htm). It is reasonable to assume that infants with birth weight less than 2.36 kilograms are most likely born preterm.

9.3.3. **Subgroups**

Within each cohort (ie, Cohort 1 and 2), 3 subgroups will be identified as follows:

- (1) Patients who have a diagnosis of GERD with EE: defined based on the presence of at least one of the ICD-9-CM or ICD-10-CM codes as shown in Table 1 and the presence of an additional ICD-9-CM or ICD-10-CM code for ulcer of the esophagus during the baseline period or on the index date, as shown in Table 1.
- (2) Patients who have a diagnosis of GERD without EE: defined based on the presence of at least one of the ICD-9-CM or ICD-10-CM codes and no ICD-9-CM or ICD-10-CM code for ulcer of esophagus during the baseline period or on the index date, as shown in Table 1.
- (3) Patients without a diagnosis of GERD or EE: defined as patients who do not have any of the ICD-9-CM or ICD-10-CM codes as shown in Table 1 during the baseline period or on the index date.

ICD-9-CM codes will be used to identify the subgroups prior to October 2015, after which ICD-10-CM codes will be used. No validated algorithm for GERD with or without EE were found to be available via literature review, therefore, a combination of clinical input, and the available codes identified in the literature will be used.² Additionally, there is no explicit ICD-9-CM code for GERD with/without esophagitis. Therefore, based on a cross-sectional study that examined the validity of diagnosis codes of benign upper gastrointestinal disorders using electronic patient records², and an online conversion tool maintained by the Center for Medicare Services and the Centers for Disease Control and Prevention (available at URL: https://icd.codes/convert/icd10-to-icd9-cm), the subgroups of GERD with or without EE will be determined using the operational definitions shown in Table 1:

Table 1. Operationalization of subgroups

Subgroup	ICD-10- CM Code	Description of ICD- 10-CM code	ICD-9- CM Code	Description of ICD-9- CM code

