9.6. Study size

There are no a priori hypotheses specified, and therefore, sample size calculations are not applicable. All eligible patients meeting inclusion/exclusion criteria will be included in the study. Based on preliminary feasibility, it is anticipated that 7,489 infants aged 1 month to <1 year and 6,657 patients aged 1 to <2 years who have been treated with IV pantoprazole will be eligible for inclusion in the study. Table 5 below shows the 95% confidence intervals around varying hypothetical frequencies of outcomes given a 7,489 and 6,657 patient sample, calculated using the Wilson score interval.

Table 5. Precision estimates for varying frequencies of outcomes for given 7,489 and 6,657 patient samples

Sample size	Outcome Frequency	N Events*	Lower 95% Bound	Upper 95% Bound
7489	0.002	15	0.0012	0.0033
	0.005	37	0.0036	0.0068
	0.01	75	0.0080	0.0125
	0.05	374	0.0452	0.0551
	0.1	749	0.0934	0.1070
	0.2	1498	0.1911	0.2092
6657	0.002	13	0.0011	0.0033
	0.005	33	0.0035	0.0070
	0.01	67	0.0079	0.0128
	0.05	333	0.0450	0.0555

10 February 2022

0.1	666	0.0931	0.1075
0.2	1331	0.1905	0.2097

^{*}Note: Event counts are rounded to nearest whole number

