9.9. Quality control

Aetion will build measures for cohort inclusion, outcomes and covariates based on codes and algorithms described in this protocol, which were collaboratively agreed upon with Pfizer. All measures created, cohorts developed, statistical analyses implemented, and tables completed will undergo quality control review by at least one additional analyst or scientist under the supervision of the Science Lead. All analyses will separately be doubly implemented by an independent team. Results of single and double implementations will be compared, and any discrepancies will be adjudicated by a third-party senior science team

member not involved in either implementation. Furthermore, the Science Lead will review all results tables to confirm accuracy, logical flow, and appropriate format. This protocol will be strictly followed when conducting the analysis of this study.

The data were subject to quality control procedures. The data provider was contacted to help rectify any problems identified during the quality control procedures, including if the files received appeared to be incomplete or the data values were implausible. The data are loaded into the Aetion Evidence Platform after minimal processing into patient longitudinal timelines to enable representation of the original data and without any data loss. Events are required to have a valid start date. Record counts are cross-checked for validation and compared to the original data counts.

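### The ICD-10-CM preterm exclusion in 9.3.2 lists P030-P039, which appears to be P07.30-P07.39 with characters lost; run as printed, it keeps some preterm infants and removes others for an unrelated code

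*Protocol*

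**What the plan says.** Protocol section 9.3.2 removes patients with listed codes recorded up to and including the index date, the codes being those "indicating a preterm birth or birth weight less than 2.36 kilograms will be excluded". The abstract gives the same purpose for both cohorts: patients with "codes indicating a preterm birth will be excluded".

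Two parallel lists carry the rule:

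- "ICD-9-CM codes: 765.01-765.08; 765.10-765.19; 765.21-765.28"
- "ICD-10-CM codes: P07.21-P07.26; P030-P039; P07.01-P07.03; P07.14-P07.18"

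On implementation, section 9.9 says "Aetion will build measures for cohort inclusion, outcomes and covariates based on codes and algorithms described in this protocol" and "This protocol will be strictly followed when conducting the analysis of this study". Section 9.3.3 dates the change of coding system, but only for the GERD subgroups: "ICD-9-CM codes will be used to identify the subgroups prior to October 2015, after which ICD-10-CM codes will be used". Amendment 1 (section 5) updated code lists for some outcomes and does not name 9.3.2 among the sections changed.

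**The concern.** One of the four ICD-10-CM ranges does not fit the rule it serves. A code list is an executable part of the protocol, so a wrong range changes who is in the cohort.

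The study has no comparator (section 9.1) and its main output is a set of absolute incidence rates, so cohort membership bears directly on the result. The fault would also act only on children whose prematurity was coded in ICD-10-CM. The second sensitivity analysis in Table 6 compares incidence between ICD-9-CM and ICD-10-CM strata, and that comparison would carry an eligibility difference as well as a coding difference.

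**Working it through.** The plan states no figure on this point, so there is none to reproduce. The check is a side-by-side reading of the lists, an expansion of the ranges as printed, and a bound on the calendar period.

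**1. The ranges side by side (section 9.3.2)**

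| List | Range | Category | Decimal point |
|---|---|---|---|
| ICD-9-CM | 765.01-765.08 | 765 | yes |
| ICD-9-CM | 765.10-765.19 | 765 | yes |
| ICD-9-CM | 765.21-765.28 | 765 | yes |
| ICD-10-CM | P07.21-P07.26 | P07 | yes |
| ICD-10-CM | P030-P039 | P03 | **no** |
| ICD-10-CM | P07.01-P07.03 | P07 | yes |
| ICD-10-CM | P07.14-P07.18 | P07 | yes |

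The ICD-9-CM list stays within one category, and the ICD-10-CM list does so apart from one entry. Deleting the characters 7 and the point from P07.30 and P07.39 gives exactly P030 and P039. The entry also stands directly after P07.2x, where P07.3x would come next. A PDF reading fault is unlikely, because the same two characters would have to vanish at both ends of one range while the other six endpoints on the line stay intact.

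**2. Expansion as printed**

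- P03.0-P03.9: 10 codes
- P07.01-P07.03: 3 codes
- P07.14-P07.18: 5 codes
- P07.21-P07.26: 6 codes

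Total: 10 + 3 + 5 + 6 = 24. None of P07.30-P07.39 is among them.

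**3. What the codes mean**

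The protocol prescribes ICD-10-CM but does not print these definitions, so this step rests on the classification itself. P07.3x is preterm newborn, 28 to 36 completed weeks. P03.x is newborn affected by other complications of labor and delivery, which indicates neither prematurity nor low birth weight. Steps 1 and 2 show the anomaly without these definitions.

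**4. Effect if run as printed**

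- Still excluded: any preterm infant with a listed P07.0x, P07.1x or P07.2x code.
- Wrongly kept: infants whose only prematurity code is P07.3x.
- Wrongly removed: infants with a P03 code and no listed P07 code.

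**5. Bound on the calendar period**

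The study period, January 2007 to December 2020, is 14 × 12 = 168 months. October 2015 to December 2020 is 3 + 60 = 63 months, and 63/168 = 37.5%. This assumes that the October 2015 switch, stated for the subgroup codes, also applies to the exclusion codes.

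The figure is an upper bound because the rule counts any code up to the index date. A child born before October 2015 can carry a 765.xx code and be excluded at a later index date. If prematurity is coded at birth (an assumption), Cohort 2 (age 1 to <2 years) contains no child born in the ICD-10-CM period until October 2016. That leaves at most 3 + 48 = 51 months (51/168 = 30.4%). All of its children are born in that period only from October 2017: 3 + 36 = 39 months (39/168 = 23.2%). Cohort 1 is mixed until about October 2016.

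**The case against.** The strongest reply is that this is a typing slip that any programmer familiar with ICD-10-CM would read as P07.30-P07.39, so the cohort may be right and only the text wrong. Section 9.9 also provides second-analyst review, independent double implementation and third-party adjudication. Part of this stands: an error in the cohort is possible, not shown. But 9.9 also says that measures are built from the protocol's codes and that the protocol is strictly followed. Two teams working from the same printed list can repeat the same mistake without any discrepancy to adjudicate.

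Four stronger readings are tempting, and the documents do not support them:

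- *Preterm infants generally stay in.* They do not; the other three P07 ranges still remove those who carry such a code.
- *37.5% of the study is affected.* Months are not patients, the protocol gives no counts by year, and step 5 shows that the period itself is overstated, most clearly for Cohort 2.
- *The ICD-10-CM rates are inflated by some percentage.* The protocol gives neither the share of infants wrongly kept nor how much their rates differ. Patients with a prior history of an outcome are removed from that outcome's analysis, which may weaken any difference. The wrongly removed infants have an unknown effect of their own.
- *The ICD-9-CM versus ICD-10-CM analysis is spoiled.* It is descriptive, concerns subgroup coding, and already allows for heterogeneity between strata. An eligibility difference is one more confounder in it.

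**Conclusion.** The point holds in a limited form. As printed, the ICD-10-CM list does not carry out the exclusion that 9.3.2 and the abstract state: one range lies outside the relevant category, and the P07.3x codes are missing altogether. This is more than a cosmetic slip, because the list determines eligibility and 9.9 ties the programming to it.

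The consequence is conditional on the range being programmed as printed. In that case some preterm infants are kept, some infants with an unrelated birth code are removed, and eligibility differs between the coding systems. Neither the number of patients nor the net effect on the incidence rates, in size or direction, can be derived from the protocol. The 63 of 168 months is only a ceiling on the affected period.

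The conclusion rests on three assumptions: the ICD-10-CM meanings of P03.x and P07.3x, the use of the October 2015 switch for exclusion codes, and P07.30-P07.39 as the intended range. The last is strongly suggested by the list itself but is for the sponsor to confirm.

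**What to change.** 1. Confirm the intended range with the sponsor, and replace P030-P039 with P07.30-P07.39 in section 9.3.2.
2. Make the same correction in the platform measure, and verify that no P03 code is used for exclusion.
3. Re-run the cohort build. If the feasibility counts in section 9.6 (7,489 and 6,657) used this list, re-run them and Table 5 as well; the protocol does not say whether they did.
4. If the check shows that the platform already uses P07.30-P07.39, only the protocol text needs correcting.

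The cost is one code-list correction and a re-run on data that section 9.7 says are already loaded. The downside is that cohort counts may shift. The change should be made before results are reported.

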8. RESEARCH QUESTION AND OBJECTIVES

Research Question: What are the incidence rates of potential safety events of interest in infants aged 1 month to <1 year and in patients aged 1 to <2 years who were treated with IV pantoprazole in the real-world setting?

Primary Objective: To estimate the incidence of the following outcomes of interest in infants aged 1 month to <1 year and patients aged 1 to <2 years with a diagnosis of GERD with or without EE and treated with IV pantoprazole:

- Agranulocytosis
- Thrombocytopenia
- Leukopenia
- Pancytopenia
- Hypersensitivity (including anaphylactic reactions and anaphylactic shock)
- Hyperlipidaemia
- Hypertriglyceridemia
- Hyponatraemia
- Hypomagnesaemia
- Hypocalcaemia
- Hypokalaemia
- Diarrhea
- Vomiting
- Abdominal distension
- Hepatobiliary injury
- Urticaria
- Angioedema
- Stevens-Johnson syndrome
- Lyell syndrome
- Erythema multiforme
- DRESS
- Tubulointerstitial nephritis
- Photosensitivity
- Peripheral edema
- Injection site thrombophlebitis

Secondary Objective 1: To estimate the incidence of the above-mentioned outcomes of interest in infants aged 1 month to <1 year and patients aged 1 to <2 years treated with IV pantoprazole without a diagnosis of GERD or EE.

Secondary Objective 2: To provide the frequency of the 25 most common diagnostic codes occurring within 30 days prior to starting or on the date of start of IV pantoprazole (ie, index date) through 90 days of the last treatment with IV pantoprazole among infants aged 1 month

090177e1996138d1\Approved\Approved On: 23-Feb-2022 16:44 (GMT)

to <1 year and patients aged 1 to <2 years with a diagnosis of GERD (regardless of EE diagnosis).

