GERD without EE*	K21.0	GERD with esophagitis	530.10, 530.11, 530.12, 530.19	Esophagitis unspecified Reflux esophagitis, Acute esophagitis, Other esophagitis
	K21.9	GERD without esophagitis	530.81	Esophageal reflux
GERD with EE	K21.0, K21.9	GERD with or without esophagitis	530.10, 530.11, 530.12, 530.19, 530.81	Esophagitis unspecified Reflux esophagitis, Acute esophagitis, Other esophagitis Esophageal reflux
	AND			
	K22.1	Ulcer of esophagus	530.2	Ulcer of esophagus

^{*} Patients with any of the listed ICD-9-CM or ICD-10-CM codes and no ICD-9-CM code of 530.2 or ICD-10-CM code of K22.1 during the baseline period or on the index date will be included in the GERD without EE subgroup.

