9.4.3.2. Comorbidities

The following comorbidities will be identified based on the presence of at least one ICD-9-CM/ICD-10-CM diagnosis code or NDC/HCPCS codes identified using all available data during the baseline period and are operationalized in Table 4.

Table 4. Operationalization of comorbidities			
History or presence of upper gastrointestinal anatomic or motor disorders	Operationalization: ICD-10-CM code	Operationalization: ICD- 9-CM code	
Esophageal strictures, webs, diverticula, or other gastroduodenal pathology seen on esophagogastroduodenoscop y	K22.2 Esophageal obstruction K57 Diverticular disease of intestine K22.5 Diverticulum of esophagus, acquired K31.5 Obstruction of duodenum Q39.3 Congenital stenosis and stricture of esophagus Q39.4 Esophageal web	530.3 Stricture and stenosis of esophagus 537.3 Other obstruction of duodenum 530.6 Diverticulum of esophagus, acquired 562 Diverticula of intestine 750.3 Congenital tracheoesophageal fistula, esophageal atresia and stenosis	
Gastrointestinal strictures of any kind	K56.69x Other intestinal obstruction K50 Crohn's Disease	555 Regional enteritis 560.9 Unspecified intestinal obstruction, Enterostenosis; of intestine or colon: obstruction, occlusion, stenosis, stricture.	
Esophageal or gastric motor disorders (eg, scleroderma)	C15 Malignant neoplasm of esophagus Z85.01 Personal history of malignant neoplasm of esophagus K31.84 Gastroparesis K91.1 Postgastric surgery	150 Malignant neoplasm of esophagus 530 Diseases of esophagus 787.1 Heartburn V10.03 Personal history of malignant neoplasm of esophagus	

		T
	syndromes K20 Esophagitis K21 Gastro-esophageal reflux disease K22 Other diseases of esophagus R12 Heartburn K30 Functional dyspepsia K23 Disorders of esophagus in diseases classified elsewhere Q39 Congenital malformations of esophagus	536.3 Gastroparesis 564.2 Postgastric surgery syndromes 750.3 Congenital tracheoesophageal fistula, esophageal atresia and stenosis 750.4 Other specified congenital anomalies of esophagus 536.8 Dyspepsia and other specified disorders of function of stomach
Barrett's esophagus	K22.7x Barrett's esophagus	530.85 Barrett's esophagus
Peptic ulcer disease, erosive gastritis and/or erosive duodenitis	K25 Gastric ulcer K26 Duodenal ulcer K27.x Peptic ulcer, site unspecified K28 Gastrojejunal ulcer	531 Gastric ulcer 532 Duodenal ulcer 533 Peptic ulcer site unspecified 534 Gastrojejunal ulcer

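### Table 1 defines GERD more broadly before October 2015 than after it, so the GERD and no-GERD subgroups are not comparable across coding eras

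*Protocol*

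**What the plan says.** The primary objective (Section 8) is set in children "with a diagnosis of GERD with or without EE and treated with IV pantoprazole". Section 9.3.3 divides each age cohort into GERD with EE, GERD without EE, and neither, using the codes in Table 1. On timing it states: "ICD-9-CM codes will be used to identify the subgroups prior to October 2015, after which ICD-10-CM codes will be used".

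One code is enough. The Table 1 footnote puts into GERD without EE "Patients with any of the listed ICD-9-CM or ICD-10-CM codes and no ICD-9-CM code of 530.2 or ICD-10-CM code of K22.1". The ICD-9-CM side lists "530.10, 530.11, 530.12, 530.19", described as "Esophagitis unspecified Reflux esophagitis, Acute esophagitis, Other esophagitis", together with 530.81 (esophageal reflux). The ICD-10-CM side lists only K21.0 and K21.9. GERD with EE needs one of these codes plus the esophageal ulcer code (530.2 or K22.1). The third subgroup requires that no Table 1 code is present.

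The reason given for the ICD-9-CM list is that "there is no explicit ICD-9-CM code for GERD with/without esophagitis". The section adds that no validated algorithm was found, and that clinical input, a validity study and an online conversion tool were used. Table 4 (Section 9.4.3.2) has the entry "K20 Esophagitis K21 Gastro-esophageal reflux disease", so the protocol treats the two categories as distinct.

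**The concern.** By Table 1's own descriptions, 530.10, 530.12 and 530.19 do not specify reflux, yet each alone makes a child a GERD patient before October 2015. Nothing equivalent qualifies afterwards. The rule for entering the primary-objective subgroups therefore changes partway through the study for a coding reason.

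Four results depend on that rule: the rates in the two GERD subgroups, which Section 9.8 pools over the whole period; the rates in the no-GERD subgroup (secondary objective 1); the list of the 25 most common codes in GERD patients (secondary objective 2); and the comparison by coding system in Table 6, which is meant to show whether the two sets of patients are comparable.

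**Working it through.** No stated figure is in dispute. The check compares the code lists, traces the children concerned through the subgroup rules, and then illustrates the possible size.

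**1. Code lists (Table 1, with Table 4 for K20 and eosinophilic esophagitis)**

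| Type of code | ICD-9-CM, before October 2015 | ICD-10-CM, from October 2015 |
|---|---|---|
| Names reflux or GERD | 530.11, 530.81: qualify | K21.0, K21.9: qualify |
| Esophagitis, reflux not specified | 530.10, 530.12, 530.19: qualify | K20: does not qualify |
| Eosinophilic esophagitis (Table 4) | 530.13: does not qualify | K20.0: does not qualify |

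Three of five qualifying ICD-9-CM codes do not name reflux, against none of two in ICD-10-CM. The eosinophilic codes are treated alike in both eras, so the mismatch is limited to the middle row.

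**2. The same child in each era**

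| Codes carried | Before October 2015 | From October 2015 |
|---|---|---|
| Esophagitis, reflux not specified; no ulcer code | GERD without EE (primary objective) | No GERD or EE (secondary objective 1) |
| Esophagitis, reflux not specified; plus ulcer code | GERD with EE (primary objective) | None of the three |

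In the last cell, K20 with K22.1 lacks the K21 code that both GERD subgroups need. K22.1 is itself a Table 1 code, so the child is also barred from the third subgroup.

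**3. The stated reason.** Table 1 itself contains 530.11 (reflux esophagitis) and 530.81 (esophageal reflux). These line up with K21.0 and K21.9. The absence of an explicit ICD-9-CM code therefore does not explain why the other three were needed.

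**4. Calendar share.** Section 9.2: "The study period will be defined from 01 January 2007 to 31 December 2020". That is 14 × 12 = 168 months. January 2007 to September 2015 is 8 × 12 + 9 = 105 months, and 105/168 = 62.5%. This is a share of months; the protocol gives no distribution of patients over time.

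**5. Illustration, with assumed inputs.** Let w be the share of ICD-9-era GERD person-time from children with only 530.10, 530.12 or 530.19, and RR their outcome rate relative to reflux-coded children. The ICD-9-era GERD rate is then multiplied by 1 − w + w × RR. If GERD person-time is spread evenly over calendar time and reflux-coded children have the same rate in both eras, the pooled factor is 0.625 × (1 − w + w × RR) + 0.375.

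| w | RR | ICD-9-era factor | Pooled factor |
|---|---|---|---|
| 5% | 2 | 1.05 | 1.03 |
| 20% | 2 | 1.20 | 1.125 |
| 30% | 0.5 | 0.85 | 0.91 |
| 30% | 3 | 1.60 | 1.375 |

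Neither w nor RR is given in the protocol. The range shows that even the direction is open.

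**The case against.** - **The codes may capture real reflux.** Unspecified does not exclude reflux, and acute describes onset, not cause. This stands. A reader might infer that the GERD subgroups contain children known to have esophagitis of another cause; the descriptions support only that reflux is not specified. A child who also carries 530.11 or 530.81 qualifies in any case.
- **The list has a basis beyond the missing explicit code.** Section 9.3.3 cites clinical input, a validity study and a conversion tool, which cannot be examined here. That may justify a broad list, but not a broad list in one era only. The preference for more sensitive algorithms in Section 9.10 concerns capture of outcomes, and the sample-size argument there is for using both coding systems. A deliberately broad definition would have included K20.
- **It is disclosed and partly handled.** Table 6 and Section 9.10 say that ICD-9-CM is less specific and plan stratification by coding system. The ICD-10-CM stratum does give GERD rates without these children. But the strata keep the unequal lists: the analysis gives no ICD-9-era rate without them and cannot separate a definition effect from a calendar-time effect. The misclassification described in Section 9.10 is mainly EE against no EE within GERD.
- **Consequences are limited.** The study is descriptive with no comparator, and the overall-cohort rates, also reported for the primary objective, do not use Table 1. Table 5's full-cohort interval at a 1% frequency (0.0080 to 0.0125) already runs from 20% below to 25% above. This stands for rare outcomes. At a 20% frequency, however, the interval (0.1911 to 0.2092 for 7,489 infants) is only about 4.5% either way, so a definition effect could exceed sampling error. The GERD subgroups are smaller, and their sizes are not given.

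**Conclusion.** The point holds as a mismatch of definitions, visible in the protocol's own tables. A single esophagitis code not specified as reflux places a child in a GERD subgroup before October 2015 and does not do so afterwards. Both GERD subgroups, secondary objectives 1 and 2, and the ICD-9-CM versus ICD-10-CM comparison rest on definitions that differ by era. Overall-cohort rates do not.

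A reader might go further and infer that GERD rates are overstated, or that every affected child moves to the no-GERD subgroup after the switch. The protocol supports neither. It gives no code-level counts or relative rates, and the assumed ranges above (w of 5% to 30%, RR of 0.5 to 3) give an ICD-9-era factor anywhere from 0.85 to 1.60. Children with an ulcer code drop out of all three subgroups instead of moving to the third. The change should be made because the definition is unequal and cheap to align, not because a bias of known size has been shown.

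**What to change.** Apply one rule in both eras in Table 1:

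- **GERD:** 530.11 or 530.81 in ICD-9-CM; K21.0 or K21.9 in ICD-10-CM. EE additionally requires 530.2 or K22.1, as now.
- **Separate group:** children whose only qualifying esophagitis codes do not specify reflux, meaning 530.10, 530.12 or 530.19 before the switch and K20 other than K20.0 after it. Report them outside both the GERD and no-GERD subgroups in both eras. Doing this only for the ICD-9-CM codes would leave K20-only children in the no-GERD subgroup after October 2015 and move the break there.
- **Sensitivity analysis:** keep the current broad Table 1 definition.

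The cost is a code-list edit, a protocol amendment and a rerun on data that Section 9.7 says are already loaded. The ICD-9-era GERD subgroup becomes somewhat smaller and loses some true GERD children coded only as unspecified esophagitis; the sensitivity analysis still shows them. The separate group also reveals the share of children affected, which is unknown at present.
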